5.1 Study Drug

5.1.1 Accountability

The investigator or designated study personnel are responsible for maintaining accurate dispensing records of the study drug. Valproic acid will be dispensed from commercial stock. All study drug must be accounted for, including study drug accidentally or deliberately destroyed. All discrepancies between amounts of study drug dispensed and amounts returned must be documented. If appropriate, drug storage, drug dispensing, and drug accountability may be delegated to the pharmacy section of the investigative site.

5.1.2 Storage

A description of the appropriate storage and shipment conditions are specified on the product label and brochure. The stored study drug supplies must be accessible to authorized staff only. The storage area must also have adequate control of temperature in order to maintain stability and potency of study drug supplies. The capsules should be stored in the original pack until use. For further information, investigators should refer to the product label.

5.1.3 Mechanism of Drug Destruction

Dispensed unused drug will be returned to the study nurse for accounting purposes. Unused drug will be destroyed per MDACC's Drug Destruction Policy for Clinical Research Protocols.

5.1.4 Possible Adverse Effects

The most frequent adverse effects following initiation of therapy for seizure disorders

are: nausea, vomiting, and indigestion. Eructation, fecal incontinence, gastroenteritis, glossitis, flatulence, hematemesis, periodontal abscess, tooth disorder, dry mouth, stomatitis, and constipation may occur.

Somnolence, asthenia, dizziness, and tremor generally are the most frequently reported adverse nervous system effects. In humans with cancer receiving 30mg/kg/day with other systemic chemotherapy agents bone marrow suppression was the primary toxicity.

Frequency of adverse effects by organ system:

>10%:

Central nervous system: Headache (>31%), somnolence (>30%), dizziness (12% to 25%), insomnia (>1% to 15%), nervousness (>1% to 11%), pain (1% to 11%)

Dermatologic: Alopecia (>1% to 24%)

Gastrointestinal: Nausea (15% to 48%), vomiting (7% to 27%), diarrhea (7% to 23%), abdominal pain (7% to 23%), dyspepsia (7% to 23%), anorexia (>1% to 12%)

Hematologic: Thrombocytopenia (1% to 24%; dose related)

Neuromuscular & skeletal: Tremor (>57%), weakness (6% to 27%)

Ocular: Diplopia (>1% to 16%), amblyopia/blurred vision (>12%)

Miscellaneous: Infection (>20%), flu-like syndrome (12%)

1% to 10%:

(>1% to <5%) **Cardiovascular:** Peripheral edema (>1% to 8%), chest pain (>1% to <5%), edema (>1% to <5%), facial edema (>1% to <5%), hypertension (>1% to <5%), hypotension (>1% to <5%), palpitation (>1% to <5%), postural hypotension (>1% to <5%), tachycardia (>1% to <5%), vasodilation (>1% to <5%), arrhythmia

Central nervous system: Ataxia (>1% to 8%), amnesia (>1% to 7%), emotional lability (>1% to 6%), fever (>1% to 6%), abnormal thinking (>6%), depression (>1% to 5%), abnormal dreams (>1% to <5%), agitation (>1% to <5%), anxiety (>1% to <5%), catatonia (>1% to <5%), chills (>1% to <5%), confusion (>1% to <5%), coordination abnormal (>1% to <5%), hallucination (>1% to <5%), malaise (>1% to <5%), personality disorder (>1% to <5%), speech disorder (>1% to <5%), tardive dyskinesia (>1% to <5%), vertigo (>1% to <5%), euphoria (1%), hypoesthesia (1%)

Dermatologic: Rash (>1% to 6%), bruising (>1% to 5%), discoid lupus erythematosus (>1% to <5%), dry skin (>1% to <5%), furunculosis (>1% to <5%), petechia (>1% to <5%), pruritus (>1% to <5%), seborrhea (>1% to <5%)

Endocrine & metabolic: Amenorrhea (>1% to <5%), dysmenorrhea (>1% to <5%), metrorrhagia (>1% to <5%), hypoproteinemia

Gastrointestinal: Weight gain (4% to 9%), weight loss (6%), appetite increased (>6%), constipation (>1% to 5%), xerostomia (>1% to 5%), eructation (>1% to <5%), fecal incontinence (>1% to <5%), flatulence (>1% to <5%), gastroenteritis (>1% to <5%), glossitis (>1% to <5%), hematemesis (>1% to <5%), pancreatitis (>1% to <5%), periodontal abscess (>1% to <5%), stomatitis (>1% to <5%), taste perversion (>1% to <5%), dysphagia, gum hemorrhage, mouth ulceration

Genitourinary: Cystitis (>1% to 5%), dysuria (>1% to 5%), urinary frequency (>1% to <5%), urinary incontinence (>1% to <5%), vaginal hemorrhage (>1% to 5%), vaginitis (>1% to <5%)

Hepatic: ALT increased (>1% to <5%), AST increased (>1% to <5%)

Local: Injection site pain (3%), injection site reaction (2%), injection site inflammation (1%)

Neuromuscular & skeletal: Back pain (>8%), abnormal gait (>1% to <5%), arthralgia (>1% to <5%), arthrosis (>1% to <5%), dysarthria (>1% to <5%), hypertonia (>1% to <5%), hypokinesia (>1% to <5%), leg cramps (>1% to <5%), myalgia (>1% to <5%), myasthenia (>1% to <5%), neck pain (>1% to <5%), neck rigidity (>1% to <5%), paresthesia (>1% to <5%), reflex increased (>1% to <5%), twitching (>1% to <5%)

Ocular: Nystagmus (1% to 8%), dry eyes (>1% to 5%), eye pain (>1% to 5%), abnormal vision (>1% to <5%), conjunctivitis (>1% to <5%)

Otic: Tinnitus (1% to 7%), ear pain (>1% to 5%), deafness (>1% to <5%), otitis media (>1% to <5%)

Respiratory: Pharyngitis (2% to 8%), bronchitis (5%), rhinitis (>1% to 5%), dyspnea (1% to 5%), cough (>1% to <5%), epistaxis (>1% to <5%), pneumonia (>1% to <5%), sinusitis (>1% to <5%)

Miscellaneous: Diaphoresis (1%), hiccups

<1%, postmarketing, and/or case reports (limited to important and/or life-threatening):

Aggression, agranulocytosis, allergic reaction, anaphylaxis, anemia, aplastic anemia, asterixis, behavioral deterioration, bilirubin increased, bleeding time altered, bone marrow suppression, bone pain, bradycardia, breast enlargement, cutaneous vasculitis, carnitine decreased, cerebral atrophy (reversible), coma (rare), dementia, encephalopathy (rare), enuresis, eosinophilia, erythema multiforme, Fanconi-like syndrome (rare, in children), galactorrhea, hematoma formation, hemorrhage, hepatic failure, hepatotoxicity, hostility, hyperactivity, hyperammonemia, hyperammonemic encephalopathy (in patients with UCD), hyperglycinemia, hypersensitivity reactions (severe, with multiorgan dysfunction), hypofibrinogenemia, hyponatremia, hypothermia, inappropriate ADH secretion, intermittent porphyria, LDH increased, leukopenia, lupus, lymphocytosis, macrocytosis, menstrual irregularities, pancytopenia, parkinsonism, parotid gland swelling, photosensitivity, platelet aggregation inhibited, polycystic ovary disease (rare), psychosis, seeing "spots before the eyes," Stevens-Johnson syndrome, suicidal behavior/ideation, thyroid function tests abnormal, toxic epidermal necrolysis (rare), urinary tract infection

BOX WARNINGS:

Hepatotoxicity

Potentially fatal hepatic failure can occur.

Usually occurs during the initial 6 months of therapy. Children <2 years of age are at considerably increased risk of developing fatal hepatotoxicity, especially those receiving multiple anticonvulsants and those with congenital metabolic disorders, severe seizure disorders accompanied by mental retardation, or organic brain disease. Above this age group, the risk of fatal hepatotoxicity decreases considerably in progressively older patient groups.

Serious fatal hepatotoxicity may be preceded by symptoms such as malaise, weakness, lethargy, facial edema, anorexia, and vomiting.

Monitor patients closely for development of any such changes.

Perform liver function tests prior to and at frequent intervals during therapy, especially during the first 6 months.

Fetal/Neonatal Morbidity and Mortality

Can produce teratogenic effects (e.g., neural tube defects such as spinal bifida).

Use in women of childbearing potential requires that potential benefits of therapy be weighed against the risk of fetal injury.

Pancreatitis

Life-threatening pancreatitis has occurred both in children and adults. Some cases described as hemorrhagic with rapid progression from initial symptoms to death. Can occur shortly after initial use as well as after several years of use. Warn patients and caregivers that abdominal pain, nausea, vomiting, and/or anorexia can be symptoms of pancreatitis that require prompt medical evaluation.

Usually discontinue the drug and initiate alternative therapy if pancreatitis is diagnosed.

5.1.5 Precautions for Treatment

VPA should not be administered to pregnant women. A negative pregnancy test should be confirmed before administration of VPA.

5.1.6 Concomitant Treatment

Use of VPA at this dose has been documented in patients receiving FEC chemotherapy and is routinely used as an anti-seizure medication among breast cancer patients receiving chemotherapy for metastatic disease. Patients currently receiving hormonal or systemic chemotherapy for metastatic disease will be eligible. Toxicity will be assessed after half of the accrual is met, and early stopping rules will be employed.

5.2 Dose Modification Summary

Attributions will be made using clinical judgment and assigned as definite probably possible etc...as per the human subjects research manual Chapter 15.001 (inside MDA).

Valproic acid serum levels will be drawn where indicated and for grade II toxicity not possibly related to other systemic treatments. Results will be reviewed by the study research nurse. Abnormally high values (increased above upper limit normal) will be reported to the treating physician, will be considered in the clinical attribution, and the patient will become unblinded and IND monitor notified. Subsequent serum monitoring will be at the discretion of the treating physician.

2. Attribution changes to above category based on best judgement with ongoing clinical evaluation and data.

[figure not shown]
Table 1 - Starting Dose Reduction Example

Dose	Toxicity (see 5.2 and 5.3)	Dose reduced by 5mg/kg/day	Calculation Example	Number of capsules
Starting dose	Dispense 250 mg capsule e.g. (70 kg pt) per day	Reduced dose	Dispense 250 mg capsule per day	Number of capsules to be taken approx. every 8 hours
15 mg/kg/day	Dispense 4 capsules 15mg/70kg/day $15 \times 70 = 1050$ Rounded down to 1000 mg = 4 capsules	10 mg/kg/day	Dispense 2 capsules 10mg/70kg/day $10 \times 70 = 700$ Rounded down to 500 mg = 2 capsules	Take one capsule every 12 hours (if this scenario were to occur this is not a protocol violation as this is an appropriate dose for such a patient)
10 mg/kg/day	Dispense 2 capsules 5 mg/70kg/day $10 \times 70 = 700$ 700 mg = 2 capsules	5 mg/kg/day	Dispense 1 capsule 5mg/70kg/day $5 \times 70 = 350$ Rounded down to 250 mg = 1 capsule	Take one capsule once a day (if this scenario were to occur this is not a protocol violation as this is an appropriate dose for such a patient)

Table 2 - Dose Reduction Example Full Dose

Dose	Toxicity (see 5.2 and 5.3)	Dose Reduced 10mg/day	Calculation Example	Number of Capsules
Original Dose	Dispensed 250 mg capsules (ie 70 Kg pt) per day	Reduced dose	Dispensed 250 mg capsules per day	Number of capsules to be taken approx. every 8 hours
30 mg/kg/day	8 (30 x 70 = 2100, rounded down to 2000mg = 8 capsules)	20mg/kg/day	5 (20 x 70 = 1400, rounded down to 1250 = 5 capsules)	Dose 1 = 2 capsules Dose 2 = 2 capsules Dose 3 = 1 capsule
20mg/kg/day	5 (20 x 70 = 1400, rounded down to 1250 = 5 capsules)	10mg/kg/day	2 (10 x 70 = 700, rounded down to 500 = 2 capsules)	Dose 1 = 1 capsule Dose 2 = 1 capsule Dose 3 = 0 capsules

Figure 1. Dose escalation- Starting dose of 15 mg/kg/day divided in 3 doses
Study drug dosing is for 10 total weeks. During treatment visits will correspond to the week the patient is actively administering drug.

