3.0 Study Plan and Overview

3.0 Study Plan and Overview

76 breast cancer patients with malignant pleural effusion will be recruited and treated with VPA or placebo for 10 weeks. Prior data suggest chronic low dose administration is ideal for HDAC inhibition. Since q3wk dosing has often been given an average of 4 cycles, 12 weeks, 10 weeks of daily treatment is in this range and is long enough to examine fluid at multiple endpoints while on treatment while minimizing the side effects and cost of the trial.

MD Anderson Cancer Center's IND office will provide monitoring for this protocol. Patients, the investigator and the research monitor will be blinded to treatment randomization.

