3.2 Patient Recruitment

Patients will be recruited for this study by working closely with Breast Medical Oncologists. Representatives from Radiation Oncology, Breast Medical Oncology and Pulmonary Medicine (i.e., the principal investigator, the co-principal investigator, co-investigators, and the research nurse) will screen and evaluate patients seen in the MD Anderson Breast Center to identify potential subjects.

When medically appropriate, catheters will be placed as per standard of care by a pulmonologist or their trained designee after signing the usual consent for this procedure. Monitoring will be standard of care as directed by the MD responsible for

placing the catheter.

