- 3.4.8 CT scan will be performed at week 10 or earlier, if clinically indicated, to determine amount of effusion and drug effect on tumor burden.
- 3.4.9 Pleural effusion will be collected at each clinic visit. Residual fluid may be stored for additional research studies (optional).

On-Study Evaluations beyond Week 10

The EQ-5D, St. George's respiratory questionnaire and the obtaining of pleural fluid samples for research purposes will cease at the end of Week 10. After the completion of 10 weeks of VPA or placebo the patient's medical record will be followed for the date of catheter removal or date of death, which ever comes first.

Study Parameters

Studies	Prior to catheter placement	Within 72 hours prior to catheter placement	Day of catheter placement	Weeks 2, 6 and 10*	Week 10	Review EMR
Physical Exam including: v/s, wt	X ³			X ³		
Medical History	X			X		
Pregnancy Test if applicable	X ^{1,3}					
Ionized Calcium	X ³					
Magnesium	X ³					
Bloodwork	X ^{2,3}			X ^{2,3}		
ECOG PS	X			X		
St. George's questionnaire	X ³			X ³		
EQ-5D	X ³			X ³		
CXR PA and LAT		X	X	X		
Patient daily documentation of pleural fluid drainage			X	X		
Patient daily documentation of VPA or placebo administration			X	X		
optional pleural fluid			X	X		
optional blood			X	X		
optional urine			X	X		
CT chest	X ⁴				X	
Serum valproic acid for grade 2 or greater AEs ⁵						
Date of pleural catheter removal or death date						X

- Serum or Urine Pregnancy test:** Required for females of child-bearing potential. Documented use of contraception, sexual abstinence, or amenorrhea for > 6 months is sufficient to document patient is not of child-bearing potential. Otherwise must be obtained prior to first dose of VPA and must be negative to enroll.
- Hematology: CBC with differential Chemistry:** Electrolytes, BUN, creatinine, glucose, albumin, alkaline phosphatase, ALT or AST, LDH, total bilirubin, amylase, lipase, magnesium and ionized calcium.
Coagulation: Prothrombin time (PT), partial thromboplastin time (PTT), and International Normalized Ratio (INR) at baseline only.
- Within 7 days of enrollment
- Baseline CT chest completed after development of effusion and within 4 weeks of enrollment.
- Draw serum valproic acid level for any grade 2 or greater adverse events.
- Evaluations may occur any time during weeks 2, 6, and 10.

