Patients will be randomized to active treatment or control stratified by lung re-expansion ($\geq 80\%$ lung re-expansion, $<80\%$ lung re-expansion), ECOG performance status (0-1, 2, 3), using the Clinical Trial Conduct website (<https://biostatsitics.mdanderson.org/ClinicalTrialConduct>), which is housed on a secure server at MDACC and maintained by the MDACC Department of Biostatistics. Access to the website will be gained through usernames and passwords provided by the MDACC Department of Biostatistics to personnel responsible for enrolling patients and reviewing and analyzing patient data. Training on the use of the Clinical Trial Conduct website to randomize and enroll patients on the study will be provided by the study statistician. Investigation Pharmacy will have access the Clinical Trial Conduct website

to review the patient assignment. The IND office will be notified if an event occurs leading to the un-blinding of the randomization.

Toxicity Monitoring

We will use the methods described by Thall et al. (1995) to monitor the rate of toxicity leading to dose reduction for patients on active treatment. Because the study is blinded to the investigators, the study statistician will monitor the toxicity monitoring rule for the active treatment arm. Toxicity data leading to dose reduction will be forwarded to the study statistician as they accrue in the form of an email with the patient study identifier and a description of the toxicity leading to dose reduction.

If the rate of toxicity leading to dose reduction for patients on active treatment is more than 25% the study will be stopped. We will enroll a minimum of 10 and a maximum of 40 patients on active treatment. We will stop the study early if $P(\text{toxicity leading to dose reduction for patient on active treatment} > 25\% | \text{data from the study}) > 0.975$. That is, given the toxicity outcomes from the patients on active treatment, if we determine that there is more than a 97.5% chance that the rate of toxicity leading to dose reduction is more than 25% we will stop the study. This decision rule gives the following stopping rule. We assume a uniform prior distribution for the rate of toxicity leading to dose-reduction. Stop the study if

[# of pts on active treatment with toxicity leading to dose reduction / # of pts evaluated]
> 6/10, 8/15, 9/20, 11/25, 13/30, 14/35, 16/40

The operating characteristics of this study design are shown in the table below.

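### Serum valproate levels are read by the patient-facing research nurse, and high values unblind the patient, in practice only on active drug

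*Combined protocol and SAP*

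**What the plan says.** On who is blinded, section 3.0 states: "Patients, the investigator and the research monitor will be blinded to treatment randomization". The research nurse is not named there, either as blinded or as unblinded.

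On serum levels, section 5.2 states: "Results will be reviewed by the study research nurse". It continues: "Abnormally high values (increased above upper limit normal) will be reported to the treating physician". Such a value is then weighed in attribution, the patient is unblinded and the IND monitor is told. Further serum monitoring is left to the treating physician.

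On the nurse's role, section 3.2 lists the people who find and assess patients: "the principal investigator, the co-principal investigator, co-investigators, and the research nurse) will screen and evaluate patients".

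On when a level is drawn, the documents give two rules. The footnote to the Study Parameters table (section 3.4) says: "Draw serum valproic acid level for any grade 2 or greater adverse events". Section 5.2 calls for a level when it is indicated, and also "for grade II toxicity not possibly related to other systemic treatments".

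Elsewhere the plan takes care to protect the blind. Section 6.0 says of the dose-reduction stopping rule: "Because the study is blinded to the investigators, the study statistician will monitor the toxicity monitoring rule for the active treatment arm". The same section gives the pharmacy sight of the assignments: "Investigation Pharmacy will have access the Clinical Trial Conduct website". For unblinding itself, the only safeguard in section 6.0 is that the IND office is notified.

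**The concern.** In a placebo-controlled trial that excludes current valproate users (4.2.17), a serum valproate level comes close to being the randomisation code. Here it is read by someone in contact with both patients and investigators, and a high value opens the blind by rule. Because a high value can in practice arise only on active drug, the formal unblinding is one-sided.

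Several outcomes leave room for knowledge of the arm to act:

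- **Primary endpoint.** The event is removal because drainage is no longer needed. It depends on volumes that patients record at home (3.4.1), followed by a clinical and radiographic judgement (7.1). Whether a removal counts as an event depends on the reason given for it (6.0).
- **Symptoms.** EQ-5D and the St George's questionnaire are self-reported.
- **Toxicity.** High levels feed into attribution by design.

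Section 6.0 describes no analysis that takes account of unblinded patients.

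**Working it through.** The documents state no figure for draws or unblindings, so there is none to reproduce. The check has three parts: what a level discloses and to whom, how many patients this could touch, and whether the two triggers agree.

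**1. What a level discloses, and to whom**

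- *Measurable level.* Entry excludes current users (4.2.17), so this points to active drug.
- *Absent level.* This suggests placebo but does not prove it. Missed doses or an interruption could give the same result on active drug. The reduction example in section 5.2 goes down to one 250 mg capsule a day, and adherence is checked by a returned diary (5.0).
- *Level at or below the upper limit.* It stops with the nurse, and no section passes it on. The nurse is outside the list in section 3.0, so her or his knowledge does not breach the stated blind. It does place the arm one conversation away from people who are blinded.
- *Level above the upper limit.* It goes to the treating physician and the patient is unblinded. Section 3.0 says patients and the investigator are blinded, and section 5.2 makes no reference to that rule. The documents do not say whether the treating physician counts as the investigator, whether the IND monitor is the blinded research monitor, or whether the patient is actually told.

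**2. How many patients**

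The documents supply 38 patients per arm and 76 in total (6.0). They do not give the share of patients drawn or the laboratory's upper limit. Section 1.2.1 reports plasma levels of 73.6 to 170.49 µg/mL in a phase I study at 20 to 40 mg/kg, but without an upper limit this gives no rate of high values. The rates below are therefore assumptions, not tied to either trigger:

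- active patients with a level drawn: 20% to 60%
- placebo patients with a level drawn: 10% to 30%
- drawn active patients with a high value: 20% to 50%

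Patients whose arm the nurse could infer = 38 × share drawn, by arm:

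- active: 38 × 0.20 = 7.6 to 38 × 0.60 = 22.8, or about 8 to 23
- placebo: 38 × 0.10 = 3.8 to 38 × 0.30 = 11.4, or about 4 to 11
- together: 8 + 4 = 12 to 23 + 11 = 34 of 76 (11.4 to 34.2 before rounding)

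Formally unblinded = 38 × share drawn × share high:

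- active: 38 × 0.20 × 0.20 = 1.5 to 38 × 0.60 × 0.50 = 11.4, which is 4% to 30% of the arm
- placebo: essentially 0

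**3. The two triggers**

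The schedule footnote covers every event of grade 2 or above, whatever its cause. Section 5.2 covers grade II toxicity only when it is not possibly due to other systemic treatment, plus an undefined category of indicated draws. The caption of Figure 7 (5.3.1.1) follows the section 5.2 wording. Patients on chemotherapy or hormonal treatment are eligible (5.1.6), so the two rules could produce very different numbers of draws. The management figures are not shown in the text available, so how they direct draws cannot be checked.

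**The case against.** The strongest reply is that the nurse acts as a filter. The nurse is not a blinded role, only high values travel further, and no section makes the nurse an assessor of the endpoint. Catheter monitoring belongs to the physician who placed the catheter (3.2). Removal follows numeric rules: at most 150 ml on three consecutive days, then on three alternate-day drainages, before the clinical and radiographic check (7.1). Unblinding a patient with toxicity and a high level is a safety choice with notification attached. Unblinding the patient may also mean only that the assignment is opened, not that the patient is told.

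Much of this stands. Leakage from the nurse is inferred, not documented, and the drainage thresholds narrow the room for bias in the primary endpoint. They do not close it, because the volumes are recorded by the patient and the last step is a judgement. The reply also leaves the conflict between sections 5.2 and 3.0 unresolved, and it gives no reason why serum levels need a patient-facing reader when the toxicity rule was deliberately given to the statistician.

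A reader might infer that the blind collapses for most of the trial. For example, if 30% to 90% of patients had a grade 2 or greater event, the footnote would let the nurse learn the arm of 0.30 × 76 = 23 to 0.90 × 76 = 68 patients. The documents do not support using that as the size of the problem. It rests on the broader trigger alone and on an event rate they do not give, and it counts what an unlisted role may infer in both arms, not unblinding of people the plan says are blinded.

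**Conclusion.** The point holds with two parts of different weight. The nurse's review of levels is a leakage risk that reaches both arms. The rule for high values is a stated route to unblinding that conflicts with section 3.0 and is in practice confined to the active arm.

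On the assumed rates, the first touches about 12 to 34 of 76 patients and the second about 1.5 to 11 of 38 active patients. The true numbers depend on the draw rate, the upper limit used and which trigger is followed, none of which the documents settle.

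Bias in patient-recorded drainage, the clinical part of the removal decision, attribution and the questionnaires is possible but not shown. It would be wrong to read this as evidence that the primary result must be biased, or that an absent level identifies placebo with certainty. The mismatch between the triggers needs correcting whatever view is taken of the blinding.

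**What to change.** 1. Send all serum valproate levels to the investigational pharmacy, which already has access to assignments, instead of to the research nurse.
2. Keep levels that trigger no protocol action out of sight of the nurse, the investigator and anyone judging the endpoint.
3. Leave the existing safety reporting of high values to the treating physician unchanged.
4. State whether unblinding the patient means that the patient is told or only that the assignment is opened. Say whether the treating physician and the IND monitor are among the blinded roles. Reconcile section 5.2 with section 3.0.
5. Log each unblinding by arm and date. Add to section 6.0 a sensitivity analysis of the primary endpoint for unblinded patients, such as censoring at the unblinding date, shown beside the analysis of all randomised patients. Since nearly all would be on active drug, simply dropping them would unbalance the arms, and the censoring may itself be informative.
6. Separately, reconcile the draw trigger in the schedule footnote with that in section 5.2. Which one is right is a clinical matter for the sponsor and the investigator.

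The cost is protocol wording, a laboratory routing instruction and one extra relay step through the pharmacy.
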